7.1. Overview of Target Indication

The target indication for ACE-536 is for the treatment of anemia in patients with myelodysplastic syndromes (MDS). MDS are heterogeneous diseases characterized by abnormal proliferation and differentiation of erythropoietic precursor cells in the bone marrow, resulting in peripheral cytopenias; approximately 25-30% of patients with MDS have progression to acute myeloid leukemia (AML).^{4,5,6}

MDS is a hematologic neoplasm primarily of the elderly, with 86% of MDS cases diagnosed in individuals age \geq 60 years (median age at diagnosis, 76 years). According to the SEERS data, approximately 12,000 patients are diagnosed with MDS per year in the United States and approximately 20,000 in Europe.⁷ The incidence rate of MDS in Germany is 4.1 per 100,000,⁸ with a median age between 68 and 73 years.⁹ Looking at a subset of patients in Düsseldorf, the incidence of MDS is higher in men than women with the incidence and prevalence increasing dramatically with age.¹⁰ With the number of people over the age of 65 expected to rise over the next four decades in developed countries such as Germany, there will likely be a correlated rise in the number of patients diagnosed with MDS.¹¹

MDS classification systems have been established to address the heterogeneity of MDS. The International Prognostic Scoring System (IPSS) ([Appendix 2](#)) categorizes the different types of MDS by the number of bone marrow blasts, the number of cytopenias, and bone marrow cytogenetics to predict survival and potential progression to AML.⁶ The IPSS has four risk categories: low, intermediate-1, intermediate-2, and high. Standardized response criteria for clinical trials have been established to evaluate response to the treatment. The International Working Group (IWG) criteria is an evaluation tool often used to quantify the quality of a response to treatment and for the consideration of risk based treatment goals.¹

Therapy for MDS is based on patient age, IPSS risk category, and ECOG performance status ([Appendix 4](#)).¹² MDS can be cured by stem cell transplantation; however, most patients cannot receive the transplant due to age or limited availability of appropriate donors. Therefore, supportive care is often provided for these patients. The median survival rate for low risk MDS is 5.7 years and decreases to 3.5 years for patients with intermediate-1 risk MDS.^{6,13}

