15.2.3. Secondary Analysis

Efficacy/Pharmacodynamic Effects Analysis of Secondary Endpoints:

All efficacy analyses will be performed for the EE and mITT populations.

Efficacy will be evaluated by determining the proportion of patients who have a modified HI-E erythroid response rate based upon the IWG 2006 criteria ([Appendix 5](#)), defined as 1) A mean hemoglobin increase ≥ 1.5 g/dL over an 8-week period as compared to baseline, not influenced by RBC transfusion in NTD patients or 2) A decrease of ≥ 4 units or $\geq 50\%$ of units of RBCs transfused over a period of 8 weeks, relative to the number of units of RBCs transfused in the 8 weeks immediately prior to Cycle 1 Day 1 in TD patients.

Baseline hemoglobin will be the average of two or more measures (not influenced by RBC transfusion) performed during the screening period for study A536-03 (for patients without interruption) or study A536-05 (for patients with interruption).

Baseline units of RBCs transfused will be the 8-week period prior to study A536-03 (for patients without interruption) or study A536-05 (for patients with interruption).

The erythroid response will be summarized using both a point estimate and its exact 95% confidence interval based on binomial distribution.

No direct comparison testing with concurrent or historical controls will be performed.

Analysis of other secondary efficacy/pharmacodynamic endpoints will include:

- Time to HI-E response and duration of HI-E response as per the IWG 2006 criteria and modified IWG criteria.
- Mean RBC transfusion burden
- Rate of RBC transfusion-free period lasting \geq 8 weeks in TD patients.
- Mean hemoglobin level change in NTD patients
- Other PD endpoints including:
 - Biomarkers for iron overload/metabolism
 - Relationship of biomarkers to response
 - Rates of HI-E, HI-N and HI-P

Exploratory endpoints will include:

- Biomarkers related to the TGF β superfamily.
- Patient-reported quality of life using tools including but not limited to the FACT-An questionnaire.

All binary endpoints will be summarized using both a point estimate and its exact confidence interval based on the binomial distribution. The time-to-event type secondary endpoints will be analyzed using Kaplan-Meier method to estimate the survival curve and median time to event and 95% confidence interval.

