24.7. Appendix 7: International Working Group Response Criteria for Myelodysplastic Syndromes²⁸

Table 3. Proposed modified International Working Group response criteria for altering natural history of MDS⁷

Category	Response criteria (responses must last at least 4 wk)
Complete remission	
Bone marrow: $\leq 5\%$ myeloblasts with normal maturation of all cell lines*
 
Persistent dysplasia will be noted†
 
Peripheral blood‡
 
Hgb ≥ 11 g/dL
 
Platelets $\geq 100 \times 10^9/L$
 
Neutrophils $\geq 1.0 \times 10^9/L$†
 
Blasts 0%

Partial remission	
All CR criteria if abnormal before treatment except:
 
Bone marrow blasts decreased by $\geq 50\%$ over pretreatment but still $> 5\%$
 
Cellularity and morphology not relevant

Marrow CR†	
Bone marrow: $\leq 5\%$ myeloblasts and decrease by $\geq 50\%$ over pretreatment†
 
Peripheral blood: if HI responses, they will be noted in addition to marrow CR†

Stable disease	
Failure to achieve at least PR, but no evidence of progression for > 8 wks

Failure	
Death during treatment or disease progression characterized by worsening of cytopenias, increase in percentage of bone marrow blasts, or progression to a more advanced MDS FAB subtype than pretreatment

Relapse after CR or PR	
At least 1 of the following:
 
Return to pretreatment bone marrow blast percentage
 
Decrement of $\geq 50\%$ from maximum remission/response levels in granulocytes or platelets
 
Reduction in Hgb concentration by ≥ 1.5 g/dL or transfusion dependence

Cytogenetic response	
Complete
 
Disappearance of the chromosomal abnormality without appearance of new ones
 
Partial
 
At least 50% reduction of the chromosomal abnormality

Disease progression	
For patients with:
 
Less than 5% blasts: $\geq 50\%$ increase in blasts to $> 5\%$ blasts
 
5%-10% blasts: $\geq 50\%$ increase to $> 10\%$ blasts
 
10%-20% blasts: $\geq 50\%$ increase to $> 20\%$ blasts
 
20%-30% blasts: $\geq 50\%$ increase to $> 30\%$ blasts
 
Any of the following:
 
At least 50% decrement from maximum remission/response in granulocytes or platelets
 
Reduction in Hgb by ≥ 2 g/dL
 
Transfusion dependence

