### **3.2. Treatment Discontinuation**

Patients will be informed that they have the right to discontinue treatment and/or withdraw from the study at any time for any reason without prejudice to their medical care.

A patient may be discontinued from treatment for any of the following reasons:

- Patient's request

- Patient's unwillingness or inability to comply with the protocol
- Pregnancy
- Use of prohibited medication (e.g., ESA)
- Medical reason or adverse event, at the discretion of the investigator and/or the medical monitor
- Lack of effect (e.g., worsening anemia for LTB patients as evidenced by sustained reduction in Hgb by  $\geq 2$  g/dL over 8 weeks or transfusion dependence), to be discussed with the medical monitor
- Disease progression (per IWG criteria for altering natural history of MDS [Cheson et al, 2006]):
  - For patients with 5-10% blasts, a 2nd bone marrow sample should be collected within 4 weeks for clinical assessment (e.g., cytomorphology, cytogenetics) to confirm progression before discontinuing patients from treatment)
- Persistent increase in white blood cell (WBC) count as per Individual Dose Modifications in protocol Section 10.8
- Presence of  $\geq 1\%$  blasts in peripheral blood as per Individual Dose Modifications in protocol Section 10.8
- Hypersensitivity reaction to study drug
- At the discretion of the sponsor (e.g., termination of the study or a dose level)

A patient may be withdrawn from the study for any of the following reasons:

- Patient's request
- Patient's unwillingness or inability to comply with the protocol
- Death
- Loss to follow-up
- At the discretion of the sponsor (e.g., termination of the study)

The reasons for study withdrawal and/or treatment discontinuation must be recorded in the patient's CRF. The investigator must notify the sponsor, the medical monitor and the contract research organization (CRO) immediately when a patient has been discontinued/withdrawn due to an AE. Patients who discontinue treatment early should complete the EOT follow-up visit at the time of discontinuation, then complete the Post-Treatment Follow-up (PTFU) visit 2 months  $\pm$  7 days after the last dose of ACE-536, the LTFU visits every 3 months, and finally the EOS visit 3 years after the last dose of ACE-536.

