## 5.8. Efficacy and Safety Analyses

No formal hypothesis testing is planned. All efficacy analyses will be performed using the ITT population.

In general, the below rules apply to the derivations of efficacy endpoints related to hemoglobin and RBC transfusion data unless specified otherwise:

- Hemoglobin measurements within 7 days following RBC transfusion will be excluded from the efficacy analysis
- For each patient, all efficacy endpoints will be derived based on an analysis cutoff day, defined as the last dose + 56 days or the last date from transfusion record data, whichever is earlier.

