#### 5.8.2.2. RBC Transfusion Independence

For patients with  $\geq 2$  units of RBC transfusion at baseline, RBC transfusion independence (RBC-TI) response is defined as not requiring RBC transfusion for 8 or more weeks while on treatment.

The proportion of RBC-TI responders will be estimated by a point estimate along with the exact 95% confidence interval based on binomial distribution. The denominator is the number of patients with  $\geq 2$  units of RBC transfusion at baseline.

Time to RBC-TI will be defined as the time from the first dose date to the starting date of the first consecutive 8-week interval not requiring RBC transfusion. Duration of RBC-TI will be calculated as the longest period of time not requiring RBC transfusion during treatment and will be censored at the analysis cutoff date for ongoing responses.

Both time to and duration of RBC-TI will be analyzed as continuous variables and summarized by descriptive statistics for RBC-TI responders only. Duration of RBC-TI will also be analyzed as a time to event variable using Kaplan-Meier method.

The derivations of RBC-TI response, time to and duration of RBC-TI will be listed for each patient.

RBC-TI responders may experience multiple periods of  $\geq 8$  weeks of RBC-TI response. For all RBC-TI responders, the number of episodes and cumulative duration will be summarized. As an exploratory analysis, the cumulative duration of the multiple responses will be analyzed using Kaplan-Meier method.

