#### **5.8.2.5. Time to and Duration of HI-E Response**

Time to and duration of HI-E response will be analyzed for HI-E responders only.

Time to HI-E response will be defined as the time from the first dose date to the first date of any rolling 8-week interval achieving HI-E response.

Duration of HI-E response will be defined as below for LTB and HTB patients, respectively:

- For LTB patients, duration of HI-E response will be calculated as the longest interval during which all hemoglobin measurements have an increase of  $\geq 1.5$  g/dL from baseline.
- For HTB patients, duration of HI-E response will be calculated for the longest such interval as the time from the start date of the first rolling 8-week interval achieving hematologic response to the end date of the last consecutive rolling 8-week interval achieving response.

When there are multiple disjoint intervals with response, the longest interval will be used. Patients with response ongoing by the analysis cutoff day will be censored at that date.

Both time to and duration of HI-E response will be analyzed as continuous variables and summarized by descriptive statistics. In addition, duration of HI-E response will also be analyzed as a time to event endpoint. The survival curves will be estimated using Kaplan-Meier method if the number of patients is more than 5.

HI-E responders may experience multiple periods of  $\geq 8$  weeks of HI-E response. For all HI-E responders, the number of episodes and cumulative duration will be summarized. As an exploratory analysis, the cumulative duration of the multiple responses will be analyzed using Kaplan-Meier method.

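### Duration of HI-E and RBC-TI response censors responders who die or stop for blast-based progression, so the Kaplan-Meier median may overstate response duration

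*SAP*

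**What the plan says.** **End of response.** Under SAP 5.8.2.5, an HI-E response in a low-transfusion-burden patient lasts while every hemoglobin value stays at least 1.5 g/dL above baseline. In a high-transfusion-burden patient it lasts while consecutive rolling 8-week intervals keep meeting the transfusion criterion. If there are several episodes, "When there are multiple disjoint intervals with response, the longest interval will be used". Then: "Patients with response ongoing by the analysis cutoff day will be censored at that date". Under SAP 5.8.2.2, duration of RBC-TI is the longest transfusion-free period on treatment and "will be censored at the analysis cutoff date for ongoing responses".

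**Cutoff.** SAP 5.8 sets the cutoff separately for each patient, "defined as the last dose + 56 days or the last date from transfusion record data, whichever is earlier".

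**What ends dosing.** SAP 3.2 and Protocol 9.3 list among the reasons to stop treatment "Disease progression (per IWG criteria for altering natural history of MDS"), a persistent rise in white-cell count, and peripheral blasts of 1% or more. Protocol 10.2.1 also has patients stop study drug if azacitidine, decitabine, lenalidomide, an ESA or G-CSF is needed.

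**Reporting.** Protocol 15.2.3 plans for time-to-event secondary endpoints the "Kaplan-Meier method to estimate the survival curve and median time to event and 95% confidence interval". The SAP asks for Kaplan-Meier curves and descriptive summaries of duration.

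**What is not said.** Neither document names death, AML or progression as an event, a censoring reason or a competing risk for these durations. No sensitivity analysis is planned. SAP 5.8.11 provides long-term survival and malignancy data as a listing only, and the table of changes in SAP 5.13 does not touch the matter.

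**The concern.** Read alone, the censoring sentence looks like ordinary administrative censoring at a data cut. Combined with the definition in SAP 5.8 it is different: the censoring date follows the patient's own last dose, and dosing often stops because of the disease. The blast, white-cell and new-therapy triggers do not require hemoglobin to fall first. A responder who leaves for one of them, and does not lose the criterion in the few weeks before the cutoff, is censored. So is a responder who dies. The cutoff definition does not mention death at all, so the status of a response in a patient who dies shortly after a dose is left to the programmer.

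Kaplan-Meier then treats these patients as if they would have gone on responding like those still under observation. Treatment can last 1825 days in a population for which the protocol itself quotes median survival of 3.5 to 5.7 years, so such exits are realistic. The resulting median is likely to be read as the expected duration of benefit, which is not what it estimates.

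**Working it through.** There is no figure to reproduce: the documents give no expected response duration, no event count and no sample-size calculation. The check therefore concerns direction, followed by an illustration of size.

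**1. Against time alive, progression-free and responding.** On the same patients and follow-up times, a composite analysis turns some censored times into events. Each Kaplan-Meier factor is then equal or smaller, so the composite curve lies on or below the planned one at every time. The planned median cannot be the shorter of the two. This needs no distributional assumption.

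**2. Illustration of that gap.**

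Inputs:
- Median survival s, from Protocol 7.1: "The median survival rate for low risk MDS is 5.7 years and decreases to 3.5 years for patients with intermediate-1 risk MDS". The exponential death hazard is ln 2 / s, or 0.122 and 0.198 per year.
- Median time to loss of criterion m: assumed to be 1, 2 or 3 years.
- Loss and death independent, both exponential.

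Formula: composite median = ln 2 / (ln 2/m + ln 2/s) = 1 / (1/m + 1/s).

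For m = 2 years:
- Low risk: 1 / (0.5 + 0.1754) = 1.48 years = 17.8 months.
- Int-1: 1 / (0.5 + 0.2857) = 1.27 years = 15.3 months.

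| Censored median | Composite, low risk | Composite, Int-1 | Ratio (1 + m/s) |
|---|---|---|---|
| 12 months | 10.2 | 9.3 | 1.18 to 1.29 |
| 24 months | 17.8 | 15.3 | 1.35 to 1.57 |
| 36 months | 23.6 | 19.4 | 1.53 to 1.86 |

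An assumed progression hazard of 0.05 per year moves the 2-year case to 1.34 (low) or 1.17 years (Int-1). At 0.10 per year it is 1.22 or 1.08. Protocol 7.1 cites progression to AML in about 25-30% of MDS patients, but without a time frame, so no hazard can be derived from it.

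**3. Against net time to loss of criterion.** A simulation (400,000 patients, 5-year limit, base median 2 years, progression hazard 0.05 per year) applied a shared gamma frailty to loss and to exit. Entries are the true net median and the Kaplan-Meier median with exits censored, in years.

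| Frailty variance | Low risk: true / KM | Int-1: true / KM |
|---|---|---|
| 0 (independent) | 2.00 / 2.00 | 2.00 / 2.00 |
| 0.5 | 2.38 / 2.61 | 2.41 / 2.75 |
| 1.0 | 2.89 / 3.52 | 2.89 / 3.87 |

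With independence there is no bias. With positive dependence the upward bias runs from about 10% (2.61/2.38) to 34% (3.87/2.89). The frailty variances are assumptions.

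**4. Against cumulative incidence of loss, with death competing.** Let λ = ln 2/m, total hazard H = λ + ln 2/s, and q = λ/H. The time at which half have lost response is -ln(1 - 0.5/q)/H. For m = 2 years:
- Low risk: H = 0.468, q = 0.740, giving 2.40 years.
- Int-1: H = 0.545, q = 0.636, giving 2.83 years.

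Here the planned 2.0 years is the shorter figure, so the direction reverses.

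**The case against.** The strongest reply is that duration until the blood-count or transfusion criterion is lost is a legitimate quantity. Appendix 5 of the protocol defines hematologic improvement by counts and transfusions alone, and Appendix 7 includes a time-to-relapse measure. Under independent censoring, Kaplan-Meier estimates that net duration without bias. A reader might infer from the 24-month row that the planned median is wrong by 35-57%. The documents do not support that: the calculation assumes independence, so those percentages separate two different quantities and do not measure error in the planned one. The reversal against cumulative incidence makes the same point. This stands, and it is why the statement must be that the median may overstate.

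Several limits also stand:
- The IWG progression definition in Protocol Appendix 7 includes "Reduction in Hgb by ≥ 2 g/dL" and transfusion dependence. Such progression would often already register as loss of response, and losses up to the cutoff count as events. The gap is mainly death and blast-based progression, not progression as a whole.
- Only patients whose longest interval is the one still ongoing are affected.
- The survival medians describe low and Int-1 MDS in general. Responders may live longer, which narrows the gap.
- These endpoints are secondary and descriptive, with no hypothesis test. Deaths, survival status and RBC-TI duration derivations are listed by patient.
- The SAP also summarizes duration as a continuous variable. Taking censored times as complete pulls those figures downward, so the reported numbers need not all err one way.

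None of this supplies the missing rule or tells the reader which duration is being reported.

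**Conclusion.** The point holds in a limited form. For both endpoints, the per-patient cutoff censors responders who die, or who stop for blast-based progression, AML or a persistent white-cell rise while still meeting the criterion. Neither document acknowledges this or plans a check on it. The Kaplan-Meier median may therefore overstate response duration. It is never below the duration alive, progression-free and responding, and it is too high for net duration if these exits go with impending loss of response, which is plausible but not shown.

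The size cannot be computed from the documents. The 24-month to roughly 15-18-month comparison shows the gap between two estimands under independent exponential hazards, the Protocol 7.1 survival medians and an assumed loss rate; it is not a trial estimate. A certain overstatement of that size, or one covering every kind of progression, goes beyond what the documents support. No test, primary endpoint or sample size is affected; what is at stake is how a descriptive median will be read.

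**What to change.** In SAP 5.8.2.2 and 5.8.2.5:

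1. Keep the loss-of-criterion analysis and state that it estimates a net duration, with death and progression censored.
2. Add, for both HI-E and RBC-TI, a Kaplan-Meier analysis in which response ends at the earliest of loss of the criterion, death, or AML or disease progression leading to discontinuation. State which date is used for each event and how a death before the cutoff is handled.
3. Report the number of responders censored by reason (death, progression or AML, other treatment stop, still on treatment at the cutoff).
4. Optionally, add cumulative incidence of loss with death and progression as competing events. Note that it answers a different question and can give a longer time than Kaplan-Meier.

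The cost is SAP wording and one extra analysis from disposition, death and follow-up data already collected. The downside is a less favourable median shown beside the planned one.

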#### 3.1. Study Design

Patients in all cohorts will receive ACE-536, administered subcutaneously (SC), every 3 weeks for up to 87 cycles or up to 1825 days, whichever occurs first. Dose titration(s), delay(s) and dose reduction(s) may be required for individual patients as outlined in the Individual Dose Modification Rules (protocol Section 10.8).

The base study A536-03 is a phase 2, open-label, ascending dose study to evaluate the effects of ACE-536 on anemia in patients with low or intermediate-1 risk MDS who are not currently receiving treatment with an erythropoiesis-stimulating agent (ESA). A total of up to 153 patients may be enrolled in the base study A536-03 and may be eligible for study A536-05.

Consenting patients that meet the A536-05 eligibility criteria may immediately roll over from A536-03 to study A536-05. These patients will forego the Post-Treatment Follow-up (PTFU) and End of Study (EOS) visits of A536-03 to begin study A536-05. For these patients, C1D1 of A536-05 may take place 28 ( $\pm$  7) days after the last dose administered in the base study A536-03, which may coincide with the patient's A536-03 End of Treatment (EOT) visit. These patients will be considered "patients without treatment interruption." Patients enrolled in expansion cohorts 2 and 3 in Study A536-03 must meet the "patients without treatment interruption" criteria to be considered for the A536-05 study, unless otherwise prospectively approved by the sponsor.

Patients who complete the EOS visit for the base study A536-03 prior to C1D1 of A536-05 are considered "patients with treatment interruption." These patients will have a 28-day screening period to allow them to be re-assessed for eligibility by meeting additional inclusion criteria, as defined in protocol Section 9.2.

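### The exploratory Kaplan-Meier analysis of cumulative response duration has no defined event, and its median depends on length of follow-up as well as on response length

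*SAP*

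**What the plan says.** SAP 5.8.2.2 recognises that "RBC-TI responders may experience multiple periods of" at least 8 weeks, and 5.8.2.5 says the same of HI-E responders. In both sections "the number of episodes and cumulative duration will be summarized", and in both a further, exploratory step is added: "the cumulative duration of the multiple responses will be analyzed using Kaplan-Meier method".

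The main duration endpoint is a different quantity. In 5.8.2.5, "When there are multiple disjoint intervals with response, the longest interval will be used", followed directly by "Patients with response ongoing by the analysis cutoff day will be censored at that date". Section 5.8.2.2 has a matching rule for the longest transfusion-free period. Neither section states an event or a censoring rule for the cumulative total.

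End of observation is set patient by patient in SAP 5.8. The analysis cutoff day is "defined as the last dose + 56 days or the last date from transfusion record data, whichever is earlier". Dosing runs "every 3 weeks for up to 87 cycles or up to 1825 days, whichever occurs first" (SAP 3.1), and lack of effect is a listed reason for stopping it (SAP 3.2; protocol 9.3). Under SAP 4.1, direct rollovers contribute A536-03 and A536-05 data, while interrupted patients contribute A536-05 data only.

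**The concern.** Kaplan-Meier needs an event that ends the duration, and censoring that is independent of the duration. Both are doubtful here.

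- **Event.** Loss of response ends an interval. It does not end a running total that resumes with the next episode. A patient between episodes at the cutoff has an open total.
- **Censoring.** For a given length of follow-up, a patient in response for more of the time is censored at a larger cumulative value. In addition, the cutoff follows the last dose, and poor response can bring the last dose forward.

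At stake is the reading of a figure in the final study report. A median cumulative duration from a survival curve will be taken as a property of the treated population and may be set beside other studies, although part of it reflects how long patients were watched. Two programmers could also code the event differently and both comply with the SAP.

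**Working it through.** The documents give no assumed episode length, gap length or median for this analysis, so there is no plan figure to reproduce. The check has three parts.

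**1. One patient, by hand.** Take a patient with 30 weeks in response, 12 weeks out, repeating (assumed; cycle 30 + 12 = 42 weeks). Apply the longest-interval rule to the total: censored if in response at cutoff, otherwise an event.

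- Cutoff at week 40: out of response, so an event at 30 weeks.
- Cutoff at week 80: out of response (weeks 72 to 84), so an event at 30 + 30 = 60 weeks.
- Cutoff at week 90: in response since week 84, so censored at 60 + 6 = 66 weeks.

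The response pattern is the same, yet the result is an event at 30, an event at 60 or censoring at 66, depending only on the cutoff. For dependent censoring, compare a second patient with 15 weeks in and 12 weeks out (cycle 27 weeks). At week 90, three cycles (81 weeks) are complete and the total is 3 × 15 + 9 = 54 weeks, censored. With the same cutoff, the better responder is censored at 66 and the other at 54.

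**2. Size, by simulation.** Inputs from the SAP are the 8-week minimum for a response and a maximum window of 1825 + 56 = 1881 days (about 269 weeks) from the first A536-05 dose. Assumed inputs are episodes of 8 weeks plus an exponential time with mean 30 weeks in total, exponential gaps with mean 12 weeks, follow-up from first response uniform on the ranges shown, and an event if out of response at cutoff. The estimator is S(t) = Π(1 − d/n), and the median is the first t with S(t) ≤ 0.5. Figures are from runs of 6,000 to 20,000 patients.

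| After each episode | Follow-up 26-104 weeks | Follow-up 104-260 weeks |
|---|---|---|
| Response always recurs | 79 to 82 weeks | 187 to 192 weeks |
| 0.3 chance of permanent loss | about 53 weeks | 69 to 71 weeks |

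Other episode shapes and starting conditions, with recurrence, gave 74 to 84 and 182 to 194 weeks.

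A second set in days (mean episode 150, mean gap 84, fixed follow-up of 365, 730, 1095 and 1881 days) gave medians of 340, 611, 873 and 1426 with recurrence. With a 0.3 chance of loss they were 262, 346, 364 and 355, against a true value of about 357.

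**3. Is follow-up all that the median reflects?** No. With 1881 days of follow-up and a 0.3 chance of loss, mean episodes of 150, 300 and 600 days gave medians of 355, 706 and 1378, against true values of 355, 706 and 1391.

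To separate the two defects, follow-up was drawn uniformly on 180 to 1881 days, independently of response, with a 0.3 chance of loss and with or without patient heterogeneity:

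- Event counted only when response is truly lost for good: bias from about −1% (361 against 366) to +4% (921 against 886).
- Longest-interval rule carried over: bias from about −7% (296 against 320) to −15% (1175 against 1388).

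The event definition is therefore the larger defect in these scenarios. The ideal event in the first line is known only in a simulation. At a real cutoff, permanent loss cannot be told from a gap, and censoring every patient who might respond again would leave no events.

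**The case against.** The strongest reply is that the curve is labelled exploratory, all summaries are descriptive (SAP 5.2), and it sits beside episode counts, descriptive totals and a Kaplan-Meier analysis of the longest single response. Nothing is tested or decided on it. That stands, and it sets the severity.

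A second reply is that with an agreed event and an independent cutoff the bias is a few per cent, so defining the event would be enough. This stands only in part: the event that gives the small bias is not observable, and the actual cutoff is not clearly independent of response.

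A third reply is that share of time in response has a similar weakness. It does. In the simulations, where time was counted from first response, the mean share went from 0.78 to 0.74 between the shorter and longer follow-up with recurrence, but from 0.67 to 0.43 with a 0.3 chance of permanent loss.

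A reader might go further and infer that the median reflects follow-up and not the drug, or that any such curve is invalid. The material does not support that. The median also rises with episode length, and where response is eventually lost and follow-up is long it settles close to the true value. Nor does the SAP state that a patient between episodes is an event. It states no rule for the cumulative total, and that rule is merely the one most readily carried over.

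**Conclusion.** The point holds. The planned Kaplan-Meier analysis of cumulative duration lacks an event that can be observed. Borrowing the longest-interval rule counts unfinished totals as finished, and censoring is related to the outcome. The median depends on length of follow-up as well as on response length: by a factor of about 2.4 (190 / 80) between the two follow-up ranges if responses keep recurring, and about 1.3 (70 / 53) if three in ten episodes end in permanent loss.

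These sizes rest on assumed episode and gap lengths, on follow-up independent of response, and on the carried-over rule. Only their direction and rough range should be relied on. Severity is low. The main analyses of longest response, and all safety analyses, are unaffected.

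**What to change.** In SAP 5.8.2.2 and 5.8.2.5, delete the sentence planning Kaplan-Meier for the cumulative duration, so that no curve or median is produced for it. Keep the number of episodes and the descriptive cumulative duration as planned, and add for responders:

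*Share of time in response = cumulative weeks in response ÷ weeks observed from first dose to the analysis cutoff day, summarised descriptively, with the distribution of weeks observed shown in the same table. First dose is the first dose in the data included for that patient under Section 4.1.*

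The last sentence matters because the observation window starts in A536-03 for direct rollovers and in A536-05 for interrupted patients.

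The cost is SAP wording before database lock and one ratio in place of one figure per endpoint; no new data are needed. The downside is small: an exploratory figure is lost, and the share still depends partly on follow-up, which is why follow-up is reported beside it.
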